3.4. Blinded data review

Prior to both the interim and final analysis, data pooled across treatment groups will be reviewed by the PATH Clinical Lead or designee for analysis decisions. The lead statistician will develop specific listings for this review and will document the Clinical Lead's decisions. Reviews will include (but not necessarily be restricted to) protocol deviations (e.g., out of window visits) for inclusion/exclusion of subjects and/or data points. The blinded review may also include clinical evaluation of safety data for reasonableness or to issue clinical queries to the site if needed. Any decisions made in blind review that might affect analysis interpretation will be documented in the Clinical Study Report (CSR).

3.5. Selection of OPA Specimens

Prior to the interim analysis of primary series immunogenicity data, the PI provided the ratio of subject enrolments per field site expected to be achieved at the completion of the trial. Based on this ratio, the independent statistician selected (based on order of entry into the study, not randomly) the first 27 subjects with evaluable V4 specimens in each treatment group from the Brikama field site, and the first 23 subjects with evaluable V4 specimens in each treatment group from the Bundung site, such that a total of 50 subjects per group were selected for OPA analysis proportional to the enrolment total in each site. Selected subjects who did not complete V5 per protocol were later replaced with new subjects from the same field site and treatment group to contribute V5 and V6 OPA data (with replacements also selected in order of enrolment date, not randomly). If more than 10% of subjects fail to contribute evaluable results at a given visit, then additional subjects may have their specimens analysed to help ensure at least 45/group contribute to each secondary functional antibody analysis timepoint. The PATH Clinical Lead will make this determination in blind review of data once the availability of OPA results has been determined for all selected subjects.

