3.2.3. Secondary Immunogenicity Objectives

The precision of IgG GMCs 4 weeks post completion of primary vaccination (V4) is expected to be as for the primary objective under the same assumptions about CV of serotype-specific IgGs and follow-up rates as previously described. The expected precision of other secondary immunogenicity objectives (IgG response rates, OPA response rates, and OPA GMTs) are as follows:

With a sample size of 220 per group (up to 10% of whom may not be evaluable), the half-width of 95% CIs for serum IgG response rates ($\text{IgG} \geq 0.35 \mu\text{g/mL}$ or $\text{IgG} \geq 1.0 \mu\text{g/mL}$) will be no more than 0.07, and the half-width of 95% CIs for differences in proportions should not exceed 0.10.

With a sample size of 50 per group (and no more than 10% excluded), the half-width of 95% CIs for OPA response rates (titer ≥ 8) will be no more than 0.15, and the half-width of 95% CIs for differences in proportions responding (PNEUMOSIL versus a comparator) should not exceed 0.21.

The VAC-056 study observed CV values that ranged from 0.97 to 2.11 for serotype-specific OPA titers measured 4 weeks after a booster dose of PNEUMOSIL in infants. Assuming the CVs for all 10 PNEUMOSIL serotypes in the current study are at most 2.11 at V4 and V6, the lower and upper 95% confidence bounds for each GMT are expected to be at most 32% below and 48% above the observed GMT based on the study size of 50 per group (assuming no more than 10% of subjects are not evaluable due to loss to follow-up or other exclusions). For example, if the observed serotype-specific GMT = 100, then the 95% CI is expected to be no wider than (68, 148). Similarly, the expected lower and upper 95% confidence bounds for descriptive GMT ratios (PNEUMOSIL versus either comparator) are expected to be no more than 42% below and 73% above the ratio. For example, if the observed GMT ratio equals 1, then the 95% CI is expected to be no wider than (0.58, 1.73), so long as the CV in the comparison group does not exceed 2.11.

Due to positive within-subject correlation among subjects contributing both V4 and V6 data, the precision of within-group booster-effects (ratios of GMCs and GMTs post-booster versus post-primary series) is expected to be at least as high as that of the between-group contrasts at V4 or V6 described above, under similar assumptions about CV and the percentage of evaluable subjects.

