3.11. Multiple Comparisons

No adjustment for multiple comparisons will be made. All descriptive CIs will be at the 95% level, and all p-values assessed for statistical significance at the two-sided 0.05 level.

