4. Within-group (booster response) GMC [GMT] ratios will be computed based on the antilog (base 10) of the mean within-subject differences in log10 concentrations [titers], V6 minus V4, restricted to subjects who contribute evaluable immunogenicity data at each time point. Confidence intervals for within-group GMC [GMT] ratios will be computed as in (3), and booster responses will be considered statistically significant if the CI excludes 1.0.

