5.3.7. Secondary Objective 7: booster responses

Secondary objective 7 is to evaluate booster responses (serum antibody response GMCs and functional response GMTs) to PNEUMOSIL, alone and in comparison to booster responses to Prevenar 13 and Synflorix, from 4 weeks after completion of primary vaccination to 4 weeks after a booster dose (restricted to a subset of 50 subjects per group for functional responses). For each serotype and treatment group, the ratio of within-group GMCs and GMTs (V6 versus V4) will be reported, together with 95% CIs for these booster responses. The totality of the data (responses at V4, V6 and booster responses) will be descriptively compared between groups for clinical relevance.

In addition to tabulations of primary and secondary endpoints, immune response data will be summarized graphically at each of V4, V5, and V6, and over time using bar charts (OPA only) and reverse cumulative distribution (RCD) curves.

Due to the impact of the COVID-19 pandemic on clinic visit schedules, not all subjects selected for the OPA analysis at V4 contributed data at V5 and V6. Per Section 3.5, subjects not contributing V5 and V6 data were replaced with new subjects from the same field site and treatment group. To assess the robustness of Secondary Objective 7 results, the analysis of this objective will be repeated when restricting the sample to subjects who contributed both V4 and V6 data. The results of this sensitivity analysis and any related exploratory analyses will be only used to guide interpretation of the primary analysis results.

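### Replacement OPA subjects are planned to give V5 and V6 titres but no V4 titre, so the V6/V4 OPA booster ratio has fewer than the stated 50 pairs in any group with a replacement, and no rule protects the number of pairs

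*SAP*

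**What the plan says.** - **Selection.** SAP 3.5 takes the first 27 and first 23 subjects per group at the two field sites, on the condition of an evaluable V4 specimen: 50 per group.
- **Replacement.** Those who did not complete V5 per protocol were "replaced with new subjects from the same field site and treatment group to contribute V5 and V6 OPA data". V4 testing of the replacements is not mentioned. SAP 3.1 describes the same replacement but triggers it on V5 or V6.
- **Top-up.** If more than 10% lack evaluable results at a visit, further specimens may be analysed "to help ensure at least 45/group contribute to each secondary functional antibody analysis timepoint". The rule is optional and has no target for subjects with two particular visits.
- **Estimator.** SAP 5.1 item 4 uses within-subject V6 minus V4 log differences, "restricted to subjects who contribute evaluable immunogenicity data at each time point". Protocol 12.7.2 has the same restriction for objective 7.
- **Stated size.** SAP 5.3.7 describes objective 7 as "restricted to a subset of 50 subjects per group for functional responses".
- **Stated precision.** SAP 3.2.3 says the precision of the booster ratio "is expected to be at least as high as that of the between-group contrasts at V4 or V6", given positive within-subject correlation and similar CV and evaluability. It gives neither a correlation nor a number of pairs.
- **Disclosure.** SAP 5.3.7 says the pandemic meant that some subjects selected at V4 gave no V5 and V6 data and were replaced. It adds a sensitivity analysis of objective 7 limited to subjects with both V4 and V6.

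**The concern.** A booster ratio needs both titres from one child. A child lost after V4 has no V6 titre; the replacement, on the plan as written, has no V4 titre. Neither forms a pair. The counts at V4, V5 and V6 can all look complete while the pairs dwindle, and the top-up rule would not notice.

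Two things are at stake. The first is precision: the OPA booster ratio would rest on fewer children than objective 7 states. The second is coherence. SAP 5.3.7 asks the reader to weigh the V4 response, the V6 response and the booster ratio together, but these would come from three sets: the initial 50, a partly different 50, and the overlap. The overlap consists only of children who came back per protocol after the disruption. The exploratory analysis of time to booster in SAP 5.3.8 also uses OPA booster ratios and would lose the same pairs.

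**Working it through.** **Inputs.** From SAP 3.2.3: "With a sample size of 50 per group (and no more than 10% excluded"), so 45 evaluable; and CVs that "in the current study are at most 2.11 at V4 and V6". From SAP 3.11: "All descriptive CIs will be at the 95% level". Not in the documents, hence assumed over a range: r, the number of initially selected subjects per group without an evaluable V4–V6 pair, and ρ, the within-child V4–V6 correlation of log titres.

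**Step 1: reproduce the SAP's figures.** The log-scale SD is s = √ln(1 + 2.11²) = 1.302.
- One GMT, n = 45: exp(± t₄₄ · s/√45) = exp(± 0.391) = 0.68 to 1.48. The SAP gives 68–148 per 100.
- Between-group ratio, 45 per group: exp(± t₈₈ · s · √(2/45)) = exp(± 0.546) = 0.58 to 1.73. The SAP gives 0.58–1.73.

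Both match.

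**Step 2: count the pairs.** Pairs = 50 − r. If r = 15 and all 15 are replaced, V4 has 50 results, V6 can have 50, and there are 35 pairs; the top-up rule is not triggered. Fifty pairs require r = 0. Forty-five require r ≤ 5.

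The 10% allowance does not secure 45 pairs. If each selected child independently had a 10% chance of lacking V6 (an assumption), the chance of at least 45 pairs out of 50 would be 0.62 in one group and 0.616³ = 0.23 in all three.

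**Step 3: precision of the paired ratio.** With m pairs the 95% CI around a ratio of 1 is exp(± t₍m−1₎ · s · √(2(1 − ρ)/m)). For example, m = 35 and ρ = 0.3 give exp(± 2.032 × 1.302 × √(1.4/35)) = exp(± 0.529) = 0.59 to 1.70.

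| Pairs (r) | ρ = 0 | ρ = 0.3 | ρ = 0.5 | Smallest ρ giving a CI no wider than 0.58–1.73 |
|---|---|---|---|---|
| 50 (0) | 0.59–1.69 | 0.65–1.55 | 0.69–1.45 | 0 |
| 45 (5) | 0.58–1.74 | 0.63–1.59 | 0.68–1.48 | 0.03 |
| 40 (10) | 0.55–1.80 | 0.61–1.64 | 0.66–1.52 | 0.14 |
| 35 (15) | 0.53–1.88 | 0.59–1.70 | 0.64–1.56 | 0.26 |
| 30 (20) | 0.50–1.99 | 0.56–1.78 | 0.61–1.63 | 0.37 |
| 25 (25) | 0.47–2.14 | 0.53–1.89 | 0.58–1.71 | 0.48 |

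The last column is 1 − (m/2) · [0.546/(t₍m−1₎ · s)]². The precision statement in SAP 3.2.3 thus depends on two quantities that the SAP does not give.

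**Step 4: set SAP 5.1 item 4 beside 5.3.7.** Under 5.1 item 4 the main analysis already uses only subjects with both visits, so the sensitivity analysis in 5.3.7 repeats it. If 5.3.7 is read as implying an unrestricted main analysis, that analysis sets V6 titres of some children against V4 titres of others, contrary to 5.1 item 4 and protocol 12.7.2. Neither reading recovers a pair.

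**The case against.** **The SAP discloses the problem.** SAP 5.3.7 reports the replacements and offers a both-visits analysis. The disclosure deserves credit, but by Step 4 the analysis is either redundant or in conflict with 5.1.

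**The shortfall may be small.** A reader might infer that the trial has fewer than 45 pairs. The documents do not show this: r is not stated, and 45 pairs survive if r is at most 5. Nor is 45 a promise about the ratio; SAP 3.5 sets it per timepoint. It would also be wrong to take a further 10% off 50 − r, because the SAP's 10% already includes loss to follow-up.

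**V4 assays of replacements are not forbidden.** This is correct. Blood is drawn from all subjects at V4, and the SAP is silent on OPA testing of the replacements' V4 sera. That none is planned is the natural reading of 3.5, not a stated rule.

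**The precision statement may still be true.** It assumes positive correlation, and at ρ = 0.5 even 25 pairs satisfy it. CV 2.11 is also the top of the quoted range (0.97–2.11). So the statement is unsupported at low pair counts, not shown to be false.

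**Conclusions may not change.** The study is descriptive, and boosters usually produce large rises. In VAC-056 (protocol Tables 9 and 11) the smallest post-booster to post-primary OPA ratio for PNEUMOSIL is for 6A, 3063.37/1317.16 = 2.33. With 25 pairs at ρ = 0.3 its lower limit would be 2.33 × 0.53 = 1.23, still above 1. Comparator ratios can be smaller. For Synflorix 19F, 1580.46/895.39 = 1.77, and the lower limit moves from 1.77 × 0.63 = 1.11 with 45 pairs to 1.77 × 0.59 = 1.04 with 35 and 1.77 × 0.53 = 0.94 with 25. These are only illustrations: that study used a three-dose primary series and OPA subsets of different sizes, and CV 2.11 is applied to the comparator by assumption.

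**Conclusion.** The concern holds in a limited form. Followed as written, the plan gives fewer than the 50 pairs stated for objective 7 in every group with a replacement, and SAP 5.3.7 confirms that replacements occurred. Forty-five pairs are not assured, because the only safeguard is optional and counts results per visit. At ρ = 0.3, going from 45 to 25 pairs widens the interval around a ratio of 1 from 0.63–1.59 to 0.53–1.89; with 25 pairs the SAP's precision statement needs ρ of about 0.48.

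This rests on the natural reading that replacements have no V4 OPA result, on CV 2.11, and on assumed values of r and ρ. It affects the OPA half of one descriptive secondary objective and the exploratory analysis built on it. IgG booster ratios are not affected, because all subjects with evaluable specimens are assayed for IgG. The contradiction between SAP 5.1 item 4 and 5.3.7 needs correcting whatever r proves to be.

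**What to change.** 1. **SAP 3.5:** choose replacements and top-up subjects who have a V4 specimen and, where residual serum allows, assay it by OPA together with their V5 and V6 sera. State the replacement trigger identically in 3.1 and 3.5.
2. **SAP 3.5:** for objective 7, set the top-up target as at least 45 evaluable V4–V6 pairs per group.
3. **SAP 5.1 and 5.3.7:** make the paired estimator primary in both. Replace the redundant sensitivity analysis with a comparison of the initially selected paired subjects and the paired set including replacements.
4. **If the V4 assays are not run:** restate the objective 7 OPA size in 5.3.7, and the precision in 3.2.3, by the actual number of pairs.

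The cost is one extra OPA run per replacement, with no new visit or blood draw, plus SAP wording. Feasibility depends on residual V4 serum: protocol Table 15 allots one 3.0 mL draw per visit to ELISA and OPA together, and what remains after ELISA is not documented. Timing also matters, because protocol 8.3 and 15.8.1 have the central laboratory destroy remaining samples once testing is complete, although 15.8.2 provides for some serum to be retained. Items 2 to 4 need no serum beyond what the top-up itself would use.

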3.6. Scheduled Study Unblinding

The requirements for scheduled unblinding for the final analysis are as follows:

1. Statistical Analysis Plan has been finalized and approved.
2. All CRF data have been collected, double-entered, and discrepancies resolved.
3. Blinded review of non-immunogenicity data is complete and corresponding analysis decisions documented.
4. Medical, concomitant medication and other text coding has been completed.
5. Non-immunogenicity analysis data sets have been independently verified.
6. Non-immunogenicity Tables and Figures programmed and verified using dummy treatment codes.

The requirements listed above will be followed to the extent possible for the planned interim analysis, noting that some queries may not be resolved at the time of the interim analysis. Any resulting implications or limitations of an incomplete blinded review will be noted in the interim analysis report. Additional details are provided in a separate Unblinding Plan.

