Version 4.0	Relevant safety analyses changed from onset of AEs within 14 days of each injection to onset within 28 days of each injection. Documented that unblinding for non-immunogenicity analyses may occur before final immunogenicity results are available. Version 4 was approved before unblinding of patient-level data.	5APR2021
Version 5.0	Modified comparative analysis of reactogenicity events to be consistent with AE summaries (use of 95% CIs for differences in proportions). Specified how to report 95% CIs when the response rate is 0% or 100% in both groups being compared. Version 5 was approved before unblinding of patient-level data.	06JUL2021

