3.13.2. Imputed Data

All immunogenicity assays reported as being below the limit of quantification or below a specified threshold will be assigned a value of one-half the lower limit of quantification (LLOQ) or threshold value, using values of LLOQ or other information provided by the responsible laboratory. Values above an applicable upper limit of quantification (ULOQ) will be assigned the ULOQ value unless determined otherwise in blind review of data.

In the event missing event dates or times are needed to compute durations of outcomes, the following rules will be applied:

- If the month and year are known, but the date is missing, the date will be imputed as the midpoint between the earliest the event could have occurred and the latest the event could have occurred, based on reporting dates and other information in the clinical data base. If data are not available to do this, the 15th will be used for any calculations of relative time (e.g., UNMAY2018, where ‘UN’ denoted unknown, would be imputed as 15MAY2018).
- If the minutes of start or stop times are missing, time will be assumed to be on the hour for a 24 hour clock (e.g., 11:UN, is assumed to be 11:00 AM).
- Listings will report unimputed dates or times.

Otherwise, no imputation for missing values is planned.

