8. APPENDIX

8.1.1. Changes to Analysis Plans after Approval of Protocol Version 1.0

- In the event of any randomization errors, supportive analyses based on the Full Immunogenicity Population will be performed according to randomized treatment assignment, rather than treatment received at enrolment. This change was implemented in Version 1.0 of the SAP, prior to any unblinding of any study team members.
- The SAP was updated throughout to reflect the change in the timing of clinic visits in response to the COVID-19 pandemic and related changes to the definition of safety endpoints (Section 2.2.1), procedures for selecting subjects contributing to OPA analysis (Section 3.5), the use of covariates (Section 3.9) in sensitivity and exploratory analyses of immunogenicity data (Sections 5.3.7 and 5.3.8), and the reporting of unsolicited TEAEs with onset after month 9 of age but before V5 (Section 5.4.2). These modifications to the SAP were made blind to individual patient treatment group assignments.
- The SAP was updated (V3) to provide further details regarding non-random selection of subjects for OPA analysis (Section 3.5) and to provide additional details regarding TEAE summaries (5.4.2). These modifications to the SAP were made blind to individual patient treatment group assignments.
- The SAP was updated (V4) to address a change in reports on timing of AE onset in relation to each vaccination (from 14 days to 28 days). Version 4 also clarified that unblinding of non-immunogenicity analyses may occur before immunogenicity results are available due to laboratory delays arising from the COVID-19 pandemic.
- The SAP was updated (V5) to address issues that arose in blind review of data. The decision was made to compare rates of REs between groups using 95% CIs for differences in proportions (rather than p-values) to be consistent with AE summaries. Also specified in the updated SAP is how to report 95% CIs when the response rate is 0% or 100% in both groups being compared, since SAS PROC FREQ does not report a result in this case.

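### Does allowing safety unblinding before the last assay results undermine the decisions that the SAP reserves for blind review?

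*SAP*

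**What the plan says.** SAP 3.6 sets six conditions for scheduled unblinding at the final analysis. The blinded review, the data-set verification and the table programming are each limited to non-immunogenicity material; for the review the words are "Blinded review of non-immunogenicity data is complete and corresponding analysis decisions documented". No condition mentions assay results. The section ends: "Additional details are provided in a separate Unblinding Plan". The Version 4.0 entry in the revision history shows that the order is intended: "Documented that unblinding for non-immunogenicity analyses may occur before final immunogenicity results are available". SAP 8.1.1 gives laboratory delays during the pandemic as the reason.

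Two later decisions depend on assay output:

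- **OPA top-up (SAP 3.5).** If more than 10% of selected subjects lack evaluable results at a visit, "additional subjects may have their specimens analysed to help ensure at least 45/group contribute". The decision falls to the Sponsor's Clinical Lead, who "will make this determination in blind review of data once the availability of OPA results has been determined for all selected subjects".
- **ULOQ rule (SAP 3.13.2).** Values above the limit "will be assigned the ULOQ value unless determined otherwise in blind review of data".

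SAP 3.4 says how blind review works: before the interim and again before the final analysis, "data pooled across treatment groups will be reviewed by the PATH Clinical Lead or designee for analysis decisions".

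**The concern.** The V4 assay results belong to the interim analysis, so the results still outstanding at final unblinding would be those from V5 and V6. Under SAP 3.6 the safety data could be unblinded while those assays were still running. SAP 3.7 sorts every listing by treatment group and screening ID, and Protocol 15.8.1 labels stored samples by screening number. Anyone holding the final safety listings could therefore identify the arm behind each assay result, and pooling the data would not blind that person.

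For the interim analysis, SAP 3.3 and 3.12 set an explicit barrier: the Sponsor receives group-level results only, with no revealing listings. The SAP does not repeat that barrier for the period between safety unblinding and the V5/V6 decisions. Protocol 7.4 mentions the Sponsor's blind only up to completion of Visit 6.

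At stake would be which subjects supply V5 and V6 OPA data (secondary objectives 1, 2, 6 and 7), how above-range values enter the geometric mean ratios, including the primary IgG ratios, and whether the study report could fairly say that these choices were made blind.

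**Working it through.** **Does the plan permit a decision with codes in hand?** The relevant texts, side by side:

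| Text | What it requires |
|---|---|
| SAP 3.6 | Unblinding does not wait for assay results |
| SAP 3.5 | OPA top-up decided in blind review |
| SAP 3.13.2 | Any ULOQ departure decided in blind review |
| SAP 3.4 | Pooled review before the final analysis |
| SAP 3.3 | Sponsor blinded to individual assignments, no end date given |
| Protocol 7.4 | Sponsor blinded until all subjects complete Visit 6 |
| Protocol 15.8.1 | Sponsor blinded until the blind is broken for the primary and secondary immunogenicity analyses |

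These can all be met together. SAP 8.1.1 says that "unblinding of non-immunogenicity analyses may occur before immunogenicity results are available". That describes staged release of analyses; it does not say that codes go to the Clinical Lead. The listing format in SAP 3.7 is a layout rule and sets no distribution schedule. Protocol 7.4 can be read as a minimum period, with Protocol 15.8.1 carrying the Sponsor's blind through to the immunogenicity analyses. The Clinical Lead is Sponsor staff and so is covered. A Clinical Lead who decided with codes in hand would breach SAP 3.5 and 3.13.2 as written.

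**How much does the OPA decision affect precision?** Inputs from SAP 3.2.3 are 50 per group, at most 10% not evaluable, and a coefficient of variation (CV) of at most 2.11.

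- Floor: 50 × (1 − 0.10) = 45 per group.
- Log-scale SD = √ln(1 + 2.11²) = 1.302.
- Limits for a geometric mean titre (GMT), n = 45: exp(±t₄₄ × 1.302/√45) = 0.676 to 1.479. The SAP's 32% below and 48% above are reproduced.
- Limits for a GMT ratio of 1, n = 45: exp(±t₈₈ × 1.302 × √(2/45)) = 0.579 to 1.726. The SAP's (0.58, 1.73) is reproduced.
- Same formula at n = 40: 0.560 to 1.786. At n = 50: 0.596 to 1.677.

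The 40 is an assumption, because the documents give no failure rate. Moving from 40 to 45 per group narrows the interval only modestly.

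**How far could a misused top-up inflate false findings?** Suppose a decider sees titres by arm, adds subjects only when the 95% interval includes 1, and keeps whichever look excludes 1. With no true difference, the correlation between the two looks is √(V₂/V₁), where V = 1/n₁ + 1/n₂. The chance that either look exceeds 1.96 in absolute value is:

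| Group sizes before → after | Correlation | Chance of a false finding |
|---|---|---|
| 44 and 45 → 45 and 45 | 0.994 | 5.5% |
| 40 and 45 → 45 and 45 | 0.970 | 6.1% |
| 35 and 45 → 45 and 45 | 0.935 | 6.7% |
| 44 and 44 → 45 and 45 | 0.989 | 5.7% |
| 40 and 40 → 45 and 45 | 0.943 | 6.6% |
| 35 and 35 → 45 and 45 | 0.882 | 7.2% |
| 35 and 35 → 50 and 50 | 0.837 | 7.6% |

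The starting counts are assumptions. These figures do not measure the concern. They require sight of results by arm and a choice between two looks, neither of which SAP 3.5 allows; the concern is only about holding treatment codes. They are not an upper limit either, because 45 per group is a floor with no cap.

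**ULOQ.** If no value exceeds the limit, the rule has no effect. The documents do not say how many values might, so no figure can be given.

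**The case for a change.** The strongest reply is that requiring blind review is a promise without a mechanism. The SAP shows that its authors knew how to supply one. For the interim they barred revealing listings, and SAP 4.2 requires decisions on deviations to be documented before unblinding. Neither safeguard extends to the V5/V6 assay decisions. The open-ended Sponsor statement in SAP 3.3 could be thought superseded once scheduled unblinding takes place. Protocol 7.4 and 15.8.1 also give different end points. The top-up is discretionary, and SAP 5.1 calls a difference statistically significant whenever the interval excludes the null value, so a choice made with knowledge of the arms could matter.

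What stands is that the supplied SAP text is silent on who holds codes in the interval, and that the two protocol statements could be aligned. Neither amounts to a missing safeguard. The absence of a repeated barrier does not cancel the requirement that these decisions be blind, and code access is a natural subject for the Unblinding Plan that SAP 3.6 cites. Protocol 12.2 also has the statistician mask participant identifiers in the deviation listings used for blind review. That does not cover the OPA or ULOQ step, but it shows that the team had a working way to prevent linkage by identifier.

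A full written barrier would also have a cost. Withholding treatment-sorted listings from the lead statistician conflicts with SAP 6.1, which has that person review the statistical package before any output goes to the Sponsor. Giving the final safety analyses to the independent statistician goes beyond the limited role in Protocol 7.4.

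**Conclusion.** No change to the plan is needed. The silence is real, but it is a gap in operational detail. A team that follows SAP 3.4, 3.5 and 3.13.2 with Protocol 15.8.1 makes both decisions blind, whether or not safety is unblinded first. Early safety unblinding is a fair response to laboratory delay.

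No bias can be derived from the documents. The OPA trigger is a count of evaluable results, the ULOQ default is fixed in advance, and the study is descriptive with no multiplicity control. Decisions on V4 data belong to the interim review and exclusions for protocol deviations are settled before unblinding, so neither is affected. SAP 3.14 does not assign the log-normality judgement to blind review, so no promise is at risk there.

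This conclusion assumes that the Clinical Lead stays within the Sponsor's blind as Protocol 15.8.1 describes, and that the Unblinding Plan, which was not available, does not say otherwise. A sentence in SAP 3.6 pointing to the relevant part of that plan would be harmless, but the results do not depend on it.
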